**Table 5 Conversion Factor for Anti-Parkinsonian Drugs**

Drug Class	Drug	Conversion Factor
Levodopa	Levodopa	x 1.00
	Levodopa Controlled Release	x 0.75
	Rytary (Carbidopa and Levodopa Extend Released)	X 0.60
	Stalevo (Carbidopa, Levodopa, and Entacapone)	x 1.33
	Duodopa A	x 1.11
COMT Inhibitors B	Entacapone	Dose of Levodopa x 0.33
	Tolacapone	Dose of Levodopa x 0.50
Nonergot-Derived Dopamine Receptor Agonists	Pramipexole	X 100.00
	Apomorphine	X 10.00
	Ropinirole	x 20.00
	Ropinirole Controlled-Release	X 20.00
	Rotigotine	x 30.00
Ergot- Derived Dopamine Receptor Agonists	Lisuride	x 100.00
	Bromocriptine	x 10.00
	Cabergoline	x 80.00
MAOB Inhibitors	Selegiline – oral	x 10.00
	Selegiline – sublingual	x 80.00
	Rasagiline	x 100.00
Other	Amantadine	x 1.00

A Duodopa is one of the prohibited medications (see protocol Section 5.7 for the complete list).

[figure not shown]
B Irrespective of the entacapone (tolcapone) dose, it is the levodopa dose that is multiplied by 0.33 (0.50 to give the LED for entacapone (tolcapone)).

COMT: Catechol-O-methyl transferase. MAOB: Monoamine oxidase type B.

## 12. SURGICAL AND MEDICAL HISTORY

Surgical and medical history are defined as those medical conditions/diseases which stopped prior to or on the date of informed consent form (ICF) signing. Chronic conditions that started prior to the signature of the ICF and are still present at the Screening visit will also be considered as surgical and medical history.

Medical history includes any prior reaction to drugs; history and treatment (if any) of cardiovascular, pulmonary, gastrointestinal, hepatic, renal, immunologic, neurologic, or psychiatric disease. It does not

include PD or sleep disorders (refer to Section 11 for summaries presented on PD and sleep disorders history).

Surgical and medical conditions/diseases will not be coded to System Organ Class (SOC) and Preferred Term (PT) using the Medical Dictionary for Regulatory Activity (MedDRA) dictionary. Hence, only a listing of the surgical and medical history will be provided. Medical conditions/diseases that are still present at the Screening visit will be flagged.

### 13. PRIOR AND CONCOMITANT MEDICATIONS

Medications will be coded using the World Health Organization (WHO) drug dictionary, version March 2015E and will be classified as follows (see APPENDIX 1 for handling of partial dates for medications.):

- **Prior medications** are defined as any medications that were started prior to the first dose of study drug
- **Concomitant medications** are defined as any medications that were taken on or after the day the first dose of study drug was taken

Prior and concomitant medications will be further classified as follows:

- PD motor functions-related medications are defined as those medications taken for the treatment of PD motor function symptoms.
- Sleep promoting medications are defined as trazodone, benzodiazepines, nonbenzodiazepines (e.g. zolpidem, zaleplon, or eszopiclone), suvorexant, melatonin receptor agonists, GABA receptor agonists opioids, and skeletal muscle relaxants (e.g. baclofen).
- Other medications will be defined as all medications other than PD motor functions and sleep promoting medications.

PD motor functions-related concomitant medications, sleep promoting concomitant medications and other concomitant medications will be summarized separately by anatomical therapeutic class (ATC) level 3 and preferred drug name based on the SAF by treatment group (including all JZP-110 doses pooled into one group) and broken down further by sequence for the placebo treatment group. A medication will be accounted once for each treatment group/sequence during which the medication was taken.

Prior medications will be provided in subject data listings only.

Number and percentage of subjects using a primary therapy device for OSA at Baseline will be summarized based on the SAF by treatment group (including all JZP-110 doses pooled into one group) and broken down further by sequence for the placebo treatment group. For subjects who used a primary therapy device for OSA at Baseline, number and percentage of subjects who have been stable on their primary therapy device settings for at least 4 weeks prior to the Baseline visit as well as if they demonstrated adequate compliance on their OSA device during the same period will be summarized similarly. Number and percentage of subjects who demonstrated adequate compliance with OSA therapy since last visit will be also provided similarly based on the SAF for each post-Baseline visit.

## 14. STUDY DRUG EXPOSURE

Exposure to study drug, in days, will be summarized overall and by sequence across all periods and by period based on the SAF. Exposure will also be summarized by treatment group (including all JZP-110 doses pooled into one group) and broken down further by sequence for the placebo treatment group based on the mITT. Interruptions, treatment compliance, and dose changes will not be taken into account for duration of exposure.

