### **5.2. MODIFIED INTENT-TO-TREAT POPULATION**

[figure not shown]
The modified intent-to-treat population (mITT) will contain all randomized subjects who received at least one dose of study drug and have a Baseline and at least one post-Baseline efficacy assessment. This analysis population will be used to perform the primary analysis of the key and exploratory efficacy endpoints (refer to Sections 16.1.4 and 16.2.3, respectively). It will also be used to summarize subjects' demographic and other Baseline characteristics, exposure to study drug, and treatment compliance data. For summaries and analyses presented based on the mITT, subjects will be classified according to randomized treatment group. If a subject in the mITT population has missing data on a specific endpoint that would require exclusion from an analysis, that subject will be excluded in the analysis of that endpoint only.

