## **5.5. SAFETY POPULATION**

The safety population (SAF) will include all subjects who took at least one dose of study drug. This analysis population will be used to summarize subjects' demographic and other Baseline characteristics, disease history, medical/surgical history, concomitant medications, exposure to study drug, treatment compliance, and safety data. For summaries presented based on the SAF, subjects will be classified according to the treatment received.

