## 15. STUDY DRUG COMPLIANCE

During the first 6 days of each treatment period, subjects will take once-daily, oral doses of study drug (75, 150, or 300 mg of JZP 110, or placebo) with water at home. On the last day of each treatment period (i.e., Days 7, 14, 21, and 28), subjects will return to the study center where they will take their study drug for that day.

Study drug will be dispensed in blister cards and collected at clinic visits. Each blister card will contain nine (9) tablets. Drug accountability will be assessed at each clinic visit based on the day of the visit and the amount of study drug that is returned to the site.

The study drug compliance of a subject will be categorized as <75%, 75%-100%, >100%-120%, or >120%.

Summary statistics and thresholds for treatment compliance will be presented overall and by sequence across all periods and by period based on the SAF. Compliance will also be summarized by treatment group (including all JZP-110 doses pooled into one group) and broken down further by sequence for the placebo treatment group based on the mITT. Subject listing will be provided.

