### 17. SAFETY OUTCOMES

All outputs for safety outcomes will be based on the SAF and, unless otherwise specified, presented by treatment group (JZP-110 75 mg, JZP-110 150 mg, JZP-110 300 mg, and placebo), regardless of the sequence and period. Summaries will also be presented for the pooled JZP-110 treatment groups, when applicable (i.e., incidences and shifts from Baseline), as well as by sequence for Placebo, but regardless of the period.

For subjects who received Sequence C, the following rules will be followed to compute the descriptive statistics, incidences and shifts from Baseline:

- For descriptive statistics, the average of the non-missing values collected at the end of each treatment period will be used;
- For incidences, each subject will be counted only once for each category;
- For shifts from Baseline, the worst value among the non-missing values collected at the end of each treatment period will be used.

For the summaries on the pooled JZP-110 group, the same rules than for the subjects who received Sequence C will be followed for the incidences and shifts from Baseline.

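### By-dose and pooled JZP-110 exposure is summarised only on the mITT by randomised treatment, so it may not match the by-dose safety tables, which use the safety population by treatment received

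*SAP*

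**What the plan says.** SAP 14 plans two exposure summaries. The first is on the safety population: "Exposure to study drug, in days, will be summarized overall and by sequence across all periods and by period based on the SAF". The second is laid out by dose and placebo, "including all JZP-110 doses pooled into one group) and broken down further by sequence for the placebo treatment group based on the mITT". SAP 15 divides compliance in the same way: "Summary statistics and thresholds for treatment compliance will be presented overall and by sequence across all periods and by period based on the SAF", with the by-treatment-group version on the mITT.

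The two populations differ in membership and in classification:

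- **SAF (SAP 5.5).** "The safety population (SAF) will include all subjects who took at least one dose of study drug". "For summaries presented based on the SAF, subjects will be classified according to the treatment received".
- **mITT (SAP 5.2).** Randomised subjects who "received at least one dose of study drug and have a Baseline and at least one post-Baseline efficacy assessment". "For summaries and analyses presented based on the mITT, subjects will be classified according to randomized treatment group".

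SAP 17 states: "All outputs for safety outcomes will be based on the SAF". Those outputs are by dose unless otherwise specified, with a pooled JZP-110 column for incidences and shifts. No section plans an exposure summary by dose, or for pooled JZP-110, on the SAF.

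**The concern.** A reader judging adverse event percentages by dose will look for the exposure behind each column. Here the exposure and adverse event tables carry the same column labels (75, 150 and 300 mg, pooled JZP-110, placebo) but rest on different membership and classification rules. A subject can therefore be counted in one table and not in the other, or sit under different treatments in the two. The subjects that the mITT rule can remove from the exposure table are dosed subjects who left in the first week, so their durations are short and tolerability may be why they left.

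Other parts of the SAP point towards the SAF. SAP 5.5 lists exposure among its uses. SAP 13 already presents concomitant medications by treatment group, with pooled JZP-110 and placebo by sequence, on the SAF. SAP 3.6, which lists changes from the protocol, gives no reason for putting by-dose exposure on an efficacy population.

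**Working it through.** **Who can be in the safety column but not in the exposure column**

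1. The first scheduled post-Baseline efficacy visit is Visit 3, Day 7 ± 1, at the end of Period 1. A subject who reaches a later period has normally passed it and is in the mITT, however short the exposure in that later period.
2. The omission is therefore confined to Period 1. By SAP Table 1, Period 1 is 75 mg in Sequence B and placebo in Sequences A and C. The columns affected are 75 mg, pooled JZP-110 and placebo.
3. A Period 1 leaver can still qualify for the mITT. Protocol 7.5 (Early Termination) lists no efficacy scale, but protocol 7.6 asks for the final-visit evaluations at discontinuation where possible. Protocol 6.14.5 asks the subject to return a week later, and the follow-up visit in protocol 7.4 includes the ESS. SAP 5.2 does not restrict post-Baseline assessments to the treatment periods. Omission needs no efficacy assessment at discontinuation and no follow-up ESS.
4. Separately, a subject given the wrong treatment is placed by treatment received in the safety tables and by randomised treatment in the exposure table. SAP 5.4 foresees such a deviation. For 150 and 300 mg this is normally the only source of difference.

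**Size**

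The plan's own allocation reproduces: 49 × 3/7 = 21, 49 × 3/7 = 21 and 49 × 1/7 = 7. The planned number on JZP-110 is 21 + 21 = 42.

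Assumptions, none of which the documents give: k Sequence B subjects stop after d daily doses in Period 1 with no post-Baseline efficacy assessment; all other Sequence A and B subjects take 7 days in each period; there are no dosing errors. Under the SAP 14.1 formulas each remaining subject has 7 days on each dose and 7 × 3 = 21 days on pooled JZP-110.

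- mITT: N = 42 − k, mean 7.0 days (75 mg) and 21.0 days (pooled).
- SAF, pooled: [21(42 − k) + dk]/42 = 21 − (21 − d)k/42.
- SAF, 75 mg: [7(42 − k) + dk]/42 = 7 − (7 − d)k/42.

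With d = 3:

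| k | N, SAF / mITT | 75 mg mean, SAF / mITT | Pooled mean, SAF / mITT |
|---|---|---|---|
| 0 | 42 / 42 | 7.0 / 7.0 | 21.0 / 21.0 |
| 1 | 42 / 41 | 6.9 / 7.0 | 20.6 / 21.0 |
| 2 | 42 / 40 | 6.8 / 7.0 | 20.1 / 21.0 |
| 4 | 42 / 38 | 6.6 / 7.0 | 19.3 / 21.0 |

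The mITT overstates the pooled mean by 21/20.57 − 1 = 2.1% for k = 1, 21/20.14 − 1 = 4.3% for k = 2 and 21/19.29 − 1 = 8.9% for k = 4. With d = 2 the pooled SAF means are 20.55 (k = 1) and 20.10 (k = 2), so the stopping day matters little. The 75 mg minimum is more sensitive: for any k of 1 or more it is 3 days on the SAF and 7 on the mITT.

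For scale, the plan expects 42 − 34 = 8 non-completers in Sequences A and B over four weeks. Taking k = 4 would put half of them in one sequence, in the first week, with no efficacy data at all.

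**The case against.** The strongest reply is that single-dose exposure on the SAF is already available. SAP 14.1 gives a formula by sequence and period, and under SAP Table 1 each sequence-period cell is one treatment. A Sequence B subject who stops 75 mg after 3 doses appears in the Sequence B, Period 1 cell, with the short minimum visible. This largely stands. For a single dose, N, mean and range can be rebuilt by hand, provided subjects took the assigned treatment. The median across the two cells cannot. For pooled JZP-110 no SAF summary exists: the across-period totals for Sequences A and B include the placebo week, and the SD, median and range of each subject's summed active exposure cannot be recovered from the cells.

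Second, a reader might infer that the exposure table drops early withdrawals at every dose. It does not. Someone who stops on the first day of 150 or 300 mg has normally passed Visit 3 and stays in the mITT with that short exposure counted.

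Third, a reader might infer that the adverse event percentages are distorted. They are not. They use the SAF and the treatment at onset, and no exposure-adjusted rates are planned, so exposure days enter no incidence.

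Fourth, SAP 5.2 and 5.5 list exposure and compliance under both populations, so dual presentation is intended, and mITT compliance helps in reading the efficacy results. That stands for compliance. For exposure, the dual presentation leaves out the by-dose and pooled SAF version.

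Finally, the documents give no rate for early loss without efficacy data or for dosing errors, so the magnitude is illustrative.

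**Conclusion.** The mismatch is certain on the text and probably small in effect. Exposure by dose and for pooled JZP-110 is planned only on the mITT by randomised treatment, while the by-dose and pooled safety outputs use the SAF by treatment received. If one or two Sequence B subjects leave in Period 1 after 3 doses with no post-Baseline efficacy assessment, mean pooled exposure is overstated by about 2 to 4% and N is one or two short of 42. With none, and no dosing errors, the tables agree. These figures rest on the assumed k and stopping day and on everyone else completing 7 days per period.

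The documents do not support a stronger conclusion: SAF exposure at single doses is not wholly hidden, 150 and 300 mg are not normally subject to the omission, and no adverse event incidence is affected. The correction is still worth making, because safety is the primary objective and the reader should not have to rebuild its exposure columns.

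**What to change.** In SAP 14, present the by-treatment-group exposure summary, including pooled JZP-110 and placebo by sequence, on the SAF by treatment received. Keep the mITT version as an additional table if wanted. Adding the same SAF version for compliance in SAP 15 is optional, since the mITT compliance table supports the efficacy analysis and SAF compliance by sequence and period is already planned.

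The cost is a change of population and classification in one SAP section (two if compliance is included) and in the table programs. No new data are needed, and the design and efficacy inference are untouched. Mean exposure may look slightly shorter.

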### 14.1. DERIVATIONS

For the summary by sequence across all treatment periods, the duration of exposure to study drug, in days, will be computed as follows:

(Date of last dose of study drug administered across all treatment periods – date of first dose of study drug administered across all treatment periods) + 1

For the summary by sequence and treatment periods, the duration of exposure to study drug, in days, will be computed as follows:

(Date of last dose of study drug administered during the treatment period – date of first dose of study drug administered during the treatment period) + 1

For the summary by treatment group in a single period, the duration of exposure to study drug, in days, will be computed as follows:

(Date of last dose of study drug administered for the treatment group – date of first dose of study drug administered for that treatment group) + 1

For the summary by treatment group in multiple periods (e.g. Placebo group in Sequence C or Pooled JZP-110 group), the duration of exposure to study drug, in days, will be computed as follows:

Sum of [(Date of last dose of study drug administered for the treatment group – date of first dose of study drug administered for that treatment group) + 1]

## 15. STUDY DRUG COMPLIANCE

During the first 6 days of each treatment period, subjects will take once-daily, oral doses of study drug (75, 150, or 300 mg of JZP 110, or placebo) with water at home. On the last day of each treatment period (i.e., Days 7, 14, 21, and 28), subjects will return to the study center where they will take their study drug for that day.

Study drug will be dispensed in blister cards and collected at clinic visits. Each blister card will contain nine (9) tablets. Drug accountability will be assessed at each clinic visit based on the day of the visit and the amount of study drug that is returned to the site.

The study drug compliance of a subject will be categorized as <75%, 75%-100%, >100%-120%, or >120%.

Summary statistics and thresholds for treatment compliance will be presented overall and by sequence across all periods and by period based on the SAF. Compliance will also be summarized by treatment group (including all JZP-110 doses pooled into one group) and broken down further by sequence for the placebo treatment group based on the mITT. Subject listing will be provided.

## 15.1. DERIVATIONS

For the summary by sequence across all periods, the study drug compliance will be calculated as the total number of tablets taken during the study (i.e., total number of tablets dispensed across all treatment periods – total number of tablets returned across all treatment periods) divided by the total number of tablets a subject should have taken during the study (i.e., duration of exposure to study drug in days [refer to Section 14.1] \* 1 tablet/day), expressed as a percentage:

$$\frac{(\text{Total number of tablets dispensed} - \text{Total number of tablets returned}) \text{ during the study} \times 100\%}{[\text{Duration of exposure to study drug (days) during the study} * 1 \text{ tablet/day}]}$$

For the summary by sequence and period as well as the summary by treatment group, the study drug compliance will be calculated as the total number of tablets taken during the concerned treatment group (i.e., total number of tablets dispensed at the beginning of the concerned treatment period – total number of tablets returned at the end of the concerned treatment period) divided by the total number of tablets a subject should have taken during the treatment period (i.e., duration of exposure to study drug during the treatment period, in days [refer to Section 14.1] \* 1 tablet/day), expressed as a percentage:

$$\frac{(\text{Number of tablets dispensed} - \text{Number of tablets returned}) \text{ during the treatment period} \times 100\%}{[\text{Duration of exposure to study drug (days) during the treatment period} * 1 \text{ tablet/day}]}$$

[figure not shown]
For the summary for the Pooled JZP-110 group, the study drug compliance will be calculated as the total number of tablets taken during the concerned treatment group (i.e., total number of tablets dispensed at the beginning of all JZP-110 treatment periods – total number of tablets returned at the end of all JZP-110 treatment periods) divided by the total number of tablets a subject should have taken during all JZP-110 treatment periods (i.e., duration of exposure to study drug while taking any JZP-110 doses, in days [refer to Section 14.1] \* 1 tablet/day), expressed as a percentage:

[figure not shown]
$$\frac{(\text{Number of tablets dispensed} - \text{Number of tablets returned}) \text{ during all JZP-110 treatment periods} \times 100\%}{[\text{Duration of exposure to study drug (days) while taking any JZP-110 doses} * 1 \text{ tablet/day}]}$$

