### **5.4. PER PROTOCOL POPULATION**

The per-protocol population (PP) will contain all subjects from the mITT, where subjects with major

deviations having an impact on efficacy endpoint(s) will be assessed, flagged, and excluded from this analysis population. The final list of major protocol deviations resulting in exclusion of subjects from the PP will be determined and approved by the sponsor prior to DBL.

Major protocol deviations resulting in exclusion of subjects from the PP may include, but are not limited to:

- Subjects not meeting the key entry inclusion/exclusion criteria
- Subjects who received the wrong treatment during a period
- Subjects with major protocol deviation(s) related to prohibited medications
- Subjects with major protocol deviation(s) related to study drug non-compliance

This analysis population will be used to perform sensitivity analyses for the key efficacy endpoint (refer to Section 16.1.5) and exploratory efficacy endpoint (refer to Section 16.2.4).

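### Compliance is measured against the days from first to last dose taken, so permanent early stopping or a late start within a period scores 100% when unused tablets are returned

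*SAP*

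**What the plan says.** SAP 15.1 takes as numerator, for each period and treatment group, the "total number of tablets dispensed at the beginning of the concerned treatment period – total number of tablets returned at the end of the concerned treatment" in question. That count is "divided by the total number of tablets a subject should have taken during the treatment period (i.e., duration of exposure to study drug", at one tablet per day.

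The duration comes from SAP 14.1. By period it is "Date of last dose of study drug administered during the treatment period" minus the "date of first dose of study drug administered during the treatment period) + 1". Treatment groups spanning several periods, such as pooled JZP-110, use the sum of such spans. The all-period figure runs from the first to the last dose in the study ("date of first dose of study drug administered across all treatment periods) + 1"). SAP 14 adds: "Interruptions, treatment compliance, and dose changes will not be taken into account for duration of exposure".

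SAP 15 plans seven doses per period, six at home and one at the clinic, from a card of nine tablets. It uses four compliance categories: below 75%, 75% to 100%, above 100% to 120%, and above 120%. It also states: "Drug accountability will be assessed at each clinic visit based on the day of the visit", together with the drug returned. Protocol 5.9 gives the same basis. The visit day does not enter the SAP 15.1 formula.

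**The concern.** The denominator is described as what the subject was due to take, but it is built from when the subject actually took drug. Planned days before the first capsule and after the last one drop out of it. A subject who gives up on a dose, or starts it late, can then look fully compliant in the table meant to show adherence by dose.

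Safety and tolerability are the primary objective and the design is ascending-dose, so adherence at each dose is something a reader will look up. SAP 15 and SAP 15.1 also use different reference points, the visit day and the last dose date, without saying how they relate.

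**Working it through.** The documents state no compliance figure to reproduce. As a check, a full period gives 7/7 = 100%.

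**Inputs.** Seven planned doses per period and nine tablets per card (SAP 15); numerator and denominator (SAP 15.1); duration (SAP 14.1). Assumptions: a nominal 7-day period, one tablet per day while dosing, and all unused tablets returned unless stated.

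**Formula.** Compliance = 100 × (dispensed − returned) / (last dose day − first dose day + 1).

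**Within one period:**

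| Pattern | SAP figure | Against 7 planned doses |
|---|---|---|
| Stops for good after day k, k = 1 to 6 | k/k = 100% | k/7 = 14.3, 28.6, 42.9, 57.1, 71.4, 85.7% |
| Starts on day j, doses to day 7, j = 2 to 7 | (8−j)/(8−j) = 100% | (8−j)/7 = 85.7, 71.4, 57.1, 42.9, 28.6, 14.3% |
| Home doses on days 1 to k, k = 1 to 5, then the Day 7 clinic dose | (k+1)/7 = 28.6, 42.9, 57.1, 71.4, 85.7% | the same |
| Stops after day 3, card not returned | 9/3 = 300% | 3/7 = 42.9% |

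In each of the first two rows, five of the six cases are below 75% of planned doses, yet the SAP figure puts all six in the 75% to 100% category. In the third row the SAP figure is right, and four of the five cases fall below 75%.

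**Pooled JZP-110.** Sequence B, stopping after day 3 of 300 mg: (7+7+3)/(7+7+3) = 100%, against 17/21 = 81.0%.

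**All periods:**

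- Permanent stop after day 3 of Period 1: 3/3 = 100%, against 3/28 = 10.7%.
- Permanent stop after day 3 of Period 4: 24/24 = 100%, against 24/28 = 85.7%.
- Only the Day 7 dose in Period 1, then full dosing: 22/22 = 100%, against 22/28 = 78.6%.
- Stop after day 3 of Period 1, resuming in Period 2: 24/28 = 85.7%, so the gap shows.
- The same in Periods 1 and 2, resuming in Period 3: 20/28 = 71.4%, so the gap shows.

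**Withdrawals.** The 7-day comparison does not carry over to subjects who leave during a period. If the denominator ended one day after the last dose (an assumption), k/(k+1) gives 50.0, 66.7, 75.0, 80.0, 83.3 and 85.7%, with two of six below 75%. If it ended on the last-dose day, the result would still be 100%.

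**The case against.** The case for leaving the formula alone is that it measures compliance while on drug, to be read beside other tables that show early stopping. Exposure in days is summarised by period and treatment group (SAP 14), withdrawals by period with reason (SAP 9), and adverse events leading to discontinuation by treatment group (SAP 17 and 17.1.4). The last dose of each period is observed at the clinic (Protocol 6.11), so a subject who skips home doses after the first but takes the clinic dose is scored correctly. Intolerance can lead to early termination (Protocol 5.2), so few subjects may stop early and still attend the end-of-period visit. All of this stands, and it rules out the reading that early stopping is never visible.

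Three stronger readings are tempting:

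- A reader might infer that the ESS analysis is affected. A subject who attends after stopping does contribute an ESS whose 7-day recall is partly off drug. That follows from analysing scheduled assessments by nominal visit (SAP 6.3), which a new compliance denominator would not change. ESS is not scheduled at the Early Termination visit.
- A reader might infer that per-protocol exclusion will miss these subjects. SAP 5.4 lists "Subjects with major protocol deviation(s) related to study drug non-compliance" but gives no percentage. Exclusion rests on a deviation list approved by the sponsor before database lock. Site accountability uses the visit day, and Protocol 5.9 has overall compliance calculated when the trial is unblinded.
- A reader might infer that stopping will be the main form of non-compliance. The documents give no rate.

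The objection does not rescue the label. SAP 15.1 presents the denominator as tablets due, not as days on drug. The late-start case also needs no missed clinic dose: one observed capsule scores 100%.

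**Conclusion.** The point holds as an error confined to the compliance summaries. With unused tablets returned, permanent early stopping or a late start scores 100% by period, by treatment group and pooled. The all-period figure is also 100% after a permanent stop, or after a late start in Period 1. Against a nominal 7-day period, adherence of 14% to 71% is reported in the 75% to 100% category. An unreturned card errs differently, giving a figure above 120% for the same subject.

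The size depends on how many subjects start late or stop early, which the documents do not allow one to estimate. No safety or efficacy estimate is shown to change. The correction is still worth making before database lock, because SAP 15 and 15.1 use different reference points and the by-dose compliance table can be misread.

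**What to change.** In SAP 15.1, for subjects who attend the end-of-period visit, set the denominator to the scheduled dosing days from the day after the previous visit through that visit. This agrees with the dispensing rule in Protocol 6.11 and allows for the visit window of plus or minus one day. For subjects withdrawn during a period, end the denominator at the documented discontinuation or withdrawal date, so that days after a protocol-required stop are not counted as non-compliance. Sum these days for the pooled and all-period figures. Set compliance to missing when the blister card is not returned.

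The cost is SAP wording and programming. Visit dates and tablet counts are already scheduled; the withdrawal rule assumes that the termination record carries a date. Reported compliance will be somewhat lower for subjects who start late or stop early. For withdrawals the gain is limited, because a discontinuation date close to the last dose leaves the figure high.
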